8.5 Changes to the protocol and informed consent form

Study procedures will not be changed without the mutual agreement of the International Co-ordinating Investigator and AstraZeneca.

The Investigator is not to deviate from the protocol. In medical emergencies, the Investigator will use medical judgment and will remove the patient from immediate hazard. The Investigator will immediately notify the Sponsor and IRB regarding the nature of the emergency and the course of action taken. The Investigator is to notify the Sponsor of any inadvertent protocol deviations upon discovery, and is to document the deviations appropriately in the study files or on the eCRFs. The Sponsor assumes no responsibility or liability for any unapproved deviations.

If there are any substantial changes to the study protocol, then these changes will be documented in a study protocol amendment and where required in a new version of the study protocol (Revised Clinical Study Protocol).

The amendment is to be approved by the IRB and if applicable, also the national regulatory authority approval, before implementation. Local requirements are to be followed for revised protocols.

AstraZeneca will distribute any subsequent amendments and new versions of the protocol to each Principal Investigators. For distribution to Ethics Committee see Section 8.3.

If a protocol amendment requires a change to a center's ICF, AstraZeneca and the center's Ethics Committee are to approve the revised ICF before the revised form is used.

If local regulations require, any administrative change will be communicated to or approved by each Ethics Committee.

8.6 Audits and inspections

Authorized representatives of AstraZeneca, a regulatory authority, or an Ethics Committee may perform audits or inspections at the center, including source data verification. The purpose of an audit or inspection is to systematically and independently examine all study-related activities and documents, to determine whether these activities were conducted, and data were recorded, analyzed, and accurately reported according to the protocol, GCP, guidelines of the ICH, and any applicable regulatory requirements. If such an audit occurs, the Investigator agrees to allow the auditor direct access to all relevant documents and to allocate his or her time and that of the study-site personnel to the auditor to discuss findings and any relevant issues. In addition, regulatory agencies may conduct a regulatory inspection of this study. The Investigator will contact AstraZeneca immediately if contacted by a regulatory agency about an inspection at the center. The Investigator agrees to allow the inspector direct access to all relevant documents and to allocate his or her time and that of the study-site personnel to the inspector to discuss findings and any relevant issues. The Investigator will allow AstraZeneca personnel to be present as an observer during a regulatory inspection, if requested.

9 STUDY MANAGEMENT BY ASTRAZENECA

9.1 Pre-study activities

Before the first patient is entered into the study, it is necessary for a representative of AstraZeneca to visit the investigational study site to:

- Determine the adequacy of the facilities
- Determine availability of appropriate patients for the study
- Discuss with the Investigators (and other personnel involved with the study) their responsibilities with regard to protocol adherence, and the responsibilities of AstraZeneca or its representatives. This will be documented in a Clinical Study Agreement between AstraZeneca and the Investigator.

9.1.1 Study Initiation and Discontinuation

Prior to initiation of the study, the Investigator must provide the Sponsor with the following documents (copies of which must be retained by the Investigator):

- Signed original copy of the protocol acceptance statement that commits the Investigator to follow the protocol exactly and to conduct the study according to GCP.
- Original copy of the Investigator's Brochure acceptance page signed by the Investigator.
- Completed and signed original Form FDA 1572.

- Current curriculum vitae, as indicated by version date in the footer or the Investigator's signature and date. Also required is a state license for the Investigator and for other medically qualified subinvestigators.
- Signed financial disclosure forms for the Investigator and all subinvestigators listed on Form FDA 1572.
- Signed copy of the IRB approval letter that lists the approved items.
- List of the IRB members who voted on the approval, including their specialty and affiliation, or the IRB assurance numbers if the roster cannot be obtained.
- Copy of the IRB approved ICF.
- Copy of the IRB approved Authorization to Use and Disclose Protected Health Information form, consistent with HIPAA legislation, if applicable.
- Copy of the local laboratory license, certification, and reference range values for any determinations required by the protocol, if applicable.

Upon receipt of all necessary paperwork, the Sponsor will arrange for all study materials to be delivered to the clinical study site. The Sponsor has the right to terminate the study at any time for any of the following reasons:

- Nonadherence of study-site personnel to the protocol or GCP
- Unavailability of the Investigator or study-site personnel to the Sponsor's monitoring personnel or designee(s)
- Other administrative reasons

Additionally, individual patients may be excluded from the study if a medical records review indicates protocol violations or if other factors appear to jeopardize the validity of the study. Throughout the course of the study, the Investigator is to make a reasonable effort to maintain the enrollment rate that was agreed upon with the Sponsor. The Investigator will also make a reasonable effort to enroll appropriate patients. The Sponsor may elect to terminate the study at a given site if the enrollment rate lags or if significant numbers of nonevaluable patients are enrolled.

9.2 Medical supervision

Medical supervision is the responsibility of the Investigator named on Form FDA 1572. The Investigator may delegate day to day activities to a subinvestigator listed on Form FDA 1572, but retains overall responsibility for ensuring that the study is conducted properly and in accordance with the study protocol. A list will be maintained that includes all qualified persons to whom the Investigator may delegate significant study-related duties. The Investigator is responsible for ensuring that drugs and devices are available for treating

possible medical emergencies, or that emergency medical facilities are available and accessible. The Investigator is responsible for ensuring that the study is conducted according to GCP, other applicable regulatory guidelines, and sound medical practices.

9.3 Training of study-site personnel

Before the first patient is entered into the study, an AstraZeneca representative will review and discuss the requirements of the Clinical Study Protocol and related documents with the investigational staff and also train them in any study specific procedures and the WBDC system(s) utilized.

The Sponsor or designee will ensure that appropriate training relevant to the study is given to all of the staff expected to be involved in the study, and that any new information relevant to the performance of this study is forwarded to the staff involved. This training may include a review of the study protocol, instructions for eCRF completion, and a review of overall responsibilities, including drug accountability and study file maintenance.

The Principal Investigator will maintain a record of all individuals involved in the study (medical, nursing, and other staff).

9.4 Laboratory accreditation

The laboratory facility used for analysis of clinical laboratory samples must provide evidence of adequate licensure or accreditation. Copies of laboratory certification, licensure, and reference ranges (as appropriate) will be supplied to the Sponsor prior to study initiation. The Sponsor or designee should be notified of any changes in reference range values or certification/license renewal during the course of the study. If a central laboratory is used, AstraZeneca will provide a copy of accreditation for the central laboratory and related reference range values.

9.5 Data Reporting

Data for each patient will be recorded on the eCRF. An eCRF must be completed for every patient enrolled in the study. When data are complete, the Investigator or medically qualified subinvestigator listed on Form FDA 1572 will apply his/her electronic signature on the eCRF indicating he/she has reviewed and approves of the data collected on eCRF.

9.6 Monitoring of the study

During the study, an AstraZeneca representative or designee(s) will have regular contacts with the study site, including visits to:

- Provide information and support to the Investigator(s).
- Confirm that facilities remain acceptable.
- Confirm that the investigational team is adhering to the protocol, that data are being accurately and timely recorded in the eCRFs, that biological samples are handled in

accordance with the Laboratory Manual and that study drug accountability checks are being performed.

- Conduct periodic audits of all eCRFs and to review all eCRFs and corresponding portions of office, clinical, and laboratory records for each patient at each clinical study site.
- Perform source data verification (a comparison of the data in the eCRFs with the patient's medical records at the hospital or practice, and other records relevant to the study) including verification of informed consent of participating patients.- This will require direct access to all original records for each patient (eg, clinic charts). Study data reviews will be performed during routine monitoring visits, both during the study and following study completion. These visits are to provide the Sponsor with the opportunity to evaluate study progress; verify the accuracy and completeness of eCRFs; and ensure that all protocol requirements, applicable US FDA or country-specific regulations, and Investigator obligations are being fulfilled. Finally, any inconsistencies in the study records should be resolved during these visits.
- Ensure withdrawal of informed consent to the use of the patient's biological samples is reported and biological samples are identified and disposed of/destroyed accordingly, and the action is documented, and reported to the patient.

The AstraZeneca representative will be available between visits if the Investigator(s) or other staff at the center needs information and advice about the study conduct.

The Sponsor may terminate study participation by a clinical study site if study-site personnel do not follow the protocol or GCP. Additionally, individual patients may be excluded if a medical records review indicates protocol violations or if other factors appear to jeopardize the validity of the study.

9.6.1 Source data

Refer to the Clinical Study Agreement for location of source data.

9.7 Study agreements

The Principal Investigator at each center should comply with all the terms, conditions, and obligations of the Clinical Study Agreement, or equivalent, for this study. In the event of any inconsistency between this Clinical Study Protocol and the Clinical Study Agreement, the terms of Clinical Study Protocol shall prevail with respect to the conduct of the study and the treatment of patients and in all other respects, not relating to study conduct or treatment of patients, the terms of the Clinical Study Agreement shall prevail.

Agreements between AstraZeneca and the Principal Investigator should be in place before any study-related procedures can take place, or patients are enrolled.

9.7.1 Archiving of study documents

The Investigator follows the principles outlined in the Clinical Study Agreement.

Investigators will maintain adequate records for the study, including patients' eCRFs, medical records, laboratory reports, signed consent forms, drug accountability records, safety reports, information regarding patients who discontinued the study, and any other pertinent data. All records and reports will be retained by the Investigator for at least 2 years after the last approval of a marketing application in an ICH region. If the marketing application is rejected or if the marketing application is not filed, the records must be retained for 2 years following notification by the Sponsor that investigations have been discontinued and that the US FDA and other government regulatory agencies have been notified. Records should be available for copying and inspection if requested by a properly authorized employee of the US FDA or other government regulatory agency, in accordance with federal regulations. The Investigator must notify the Sponsor immediately in the event of accidental loss or destruction of any study records.

Sponsor specific essential documents will be retained at least 2 years after the last approval of a marketing application in an ICH region or at least 2 years following the formal discontinuation of clinical development of the study medication. These documents should be retained for a longer period, however, if required by applicable country regulatory requirements. For eg, patient identification codes must be retained for at least 15 years following the completion or discontinuation of the study, according to Directive 91/507/EEC.

9.8 Study timetable and end of study

The end of the study is defined as 'the last visit of the last patient undergoing the study'.

The study is expected to start in Q2 2015 and to end by Q2 2021.

The study may be terminated at individual centers if the study procedures are not being performed according to GCP, or if recruitment is slow. AstraZeneca may also terminate the entire study prematurely if concerns for safety arise within this study or in any other study with EQW.

9.9 Final report

All data, including patient characteristics, methodology, and clinical findings, will be presented in a final clinical/statistical report to be prepared by the Sponsor or designee.

10 DATA MANAGEMENT

Data management will be performed by the designated contract research organization (CRO). A data management plan outlining the data management systems, procedures, and agreements between the CRO and Sponsor will be written. The plan will be reviewed and signed off by a representative of the Sponsor's data management department.

The data collected through third-party sources will be obtained and reconciled against study data.

Clinical study data will be reported (captured) on by study site personnel on eCRFs. The eCRF data will be entered by study-site personnel and then reviewed and electronically signed by the Investigator listed on Form FDA 1572. All study-site personnel must use an electronic signature access method to enter, review, or correct study data. Electronic signature procedures shall comply with the Code of Federal Regulations (CFR) Title 21 Part II and the ICH Guidelines for GCP (Topic E6, April 2000) Section 5.5.3. Passwords and electronic signatures will be strictly confidential.

All eCRF data will be downloaded from the electronic data capture (EDC) system and reformatted into SAS data sets. The Sponsor's data management department will receive electronic transfers of laboratory data from a central laboratory as well as other data from third-party vendors as appropriate. The electronic data format of all transfers will be agreed upon with the Sponsor.

Adverse events and medical/surgical history will be classified according to the terminology of the latest version the Medical Dictionary for Regulatory Activities (MedDRA). Medications will be classified according to the AstraZeneca Drug Dictionary. All coding will be performed by the CRO.

Data queries will be raised for inconsistent, impossible, or missing data. All entries to the study database will be available in an audit trail.

The data will be validated as defined in the Data Management Plan. Quality control procedures will be applied to each stage of data handling to ensure that all data are reliable and have been processed correctly.

When all data have been coded, validated, signed and locked, clean file will be declared. Any treatment revealing data may thereafter be added and the final database will be locked.

Data associated with biological samples will be transferred to laboratories internal or external to AstraZeneca.

11 EVALUATION AND CALCULATION OF VARIABLES BY ASTRAZENECA OR ITS DELEGATE

Refer to the SAP for further details.

11.1 Calculation or derivation of efficacy variables

Refer to the SAP for further details.

11.2 Calculation or derivation of safety variables

11.2.1 Other significant adverse events (OAE)

During the evaluation of the AE data, an AstraZeneca medically qualified expert will review the list of AEs that were not reported as SAEs and AEs leading to discontinuation (DAEs). Based on the expert's judgment, significant AEs of particular clinical importance may, after consultation with the Global Patient Safety Physician, be considered other significant AEs (OAEs) and reported as such in the Clinical Study Report. A similar review of laboratory/vital signs/ECG data will be performed for identification of OAEs.

Examples of these are marked hematological and other laboratory abnormalities, and certain events that lead to intervention (other than those already classified as serious), dose reduction or significant additional treatment.

11.3 Calculation or derivation of pharmacokinetic variables

If deemed necessary, appropriate PK parameters will be calculated for each patient and summarized by treatment.

11.4 Calculation or derivation of pharmacodynamic variables

Refer to the SAP for further details.

11.4.1 Calculation or derivation of the relationship between pharmacokinetic and pharmacodynamic variables

Refer to the SAP for further details.

11.4.2 Population analysis of pharmacokinetic/pharmacodynamic variables

Refer to the SAP for further details.

12 STATISTICAL METHODS AND SAMPLE SIZE DETERMINATION BY ASTRAZENECA OR DELEGATE

12.1 Description of analysis populations

Efficacy analyses will be performed in the Intent-to-Treat (ITT) Population or in a set of evaluable patients coming from the ITT Population, ie, the Evaluable Population and/or the Per-Protocol (PP) population. The Evaluable Population will be used for the primary analysis. Safety analyses will be performed for the ITT Population unless stated otherwise.

The following populations will be used for the summaries and analyses of the study data. The populations are defined as follows:

- Intent-to-Treat (ITT): The ITT Population will consist of all randomized patients who receive at least 1 dose of randomized study medication.

- **Evaluable Population:** The Evaluable Population will consist of all ITT patients who receive at least 1 dose of study medication and have at least 1 post-baseline HbA1c assessment.
- **Per-Protocol (PP):** The per-protocol analysis set will be a subset of the ITT population through the exclusion of those with important protocol violation(s). Important protocol violations are those that have the potential to affect the result of the primary analysis. Detailed exclusion criteria for the PP population will be specified in the SAP. Patients excluded from the PP analysis will be identified before database lock.

12.2 Study endpoints

12.2.1 Primary endpoint

- Change in HbA1c from baseline Visit 2 (Week 0) to Visit 7 (Week 24)

12.2.2 Secondary endpoints

- Change in HbA1c from baseline Visit 2 (Week 0) to Visit 10 (Week 52), and to each intermediate visit as applicable
- Change in fasting plasma glucose concentration from baseline Visit 2 (Week 0) to Visit 7 (Week 24), Visit 10 (Week 52), and to each intermediate visit as applicable
- Proportions of patients achieving HbA1c goals of $\leq 6.5\%$ and $< 7.0\%$ at Visit 7 (Week 24), Visit 10 (Week 52), and at each intermediate visit
- Change in body weight from baseline Visit 2 (Week 0) to Visit 7 (Week 24), Visit 10 (Week 52), and to each intermediate visit as applicable
- Change in fasting insulin and C-peptide from baseline Visit 2 (Week 0) to Visit 7 (Week 24), Visit 10 (Week 52), and to each intermediate visit as applicable
- Change in beta-cell function (HOMA-B) and insulin sensitivity (HOMA-S) as measured by homeostasis model assessments in EQW patients not taking insulin from baseline Visit 2 (Week 0) to Visit 7 (Week 24), Visit 10 (Week 52), and to each intermediate visit as applicable
- Change in lipids from baseline Visit 2 (Week 0) to Visit 5 (Week 12), Visit 7 (Week 24), Visit 10 (Week 52), and to each intermediate visit as applicable
- Change in blood pressure from baseline Visit 2 (Week 0) to Visit 7 (Week 24), Visit 10 (Week 52), and to each intermediate visit as applicable
- Plasma exenatide concentrations at baseline Visit 2 (Week 0), Visit 7 (Week 24), Visit 10 (Week 52), and each intermediate visit, as applicable

- Proportions of patients discontinuing the study, needing rescue due to failure to maintain glycemic control, and number of rescue episodes at Visit 7 (Week 24), Visit 10 (Week 52), and at each intermediate visit
- Proportions of patients reporting different injection site reactions at Visit 3 (Week 4) through Visit 10 (Week 52).

12.2.3 Exploratory endpoints

- Change in BMI from baseline Visit 2 (Week 0) to Visit 7 (Week 24), Visit 10 (Week 52), and to each intermediate visit
- Change in body weight percentile and height percentile from baseline Visit 2 (Week 0) to Visit 7 (Week 24), Visit 10 (Week 52), and to each intermediate visit. The height and weight percentile will be determined based on the standardized growth chart for boys and girls (developed by the National Center for Health Statistics in collaboration with the National Center for Chronic Disease Prevention and Health Promotion ([Center for Disease Control and Prevention, 2010](#))).

12.2.4 Safety endpoints

- Safety and tolerability endpoints including the incidence of treatment emergent AEs, antibodies to exenatide, physical examinations, laboratory measurements (clinical, chemistry/hematology), and vital sign measurements from baseline Visit 2 (Week 0) to Visit 7 (Week 24), Visit 10 (Week 52), and to each intermediate visit as applicable
- Change in calcitonin, pancreatic amylase, and lipase from baseline Visit 2 (Week 0) to Visit 5 (Week 12) and Visit 10 (Week 52)
- Change in TSH, free T4, prolactin, cortisol, IGF-1, and DHEAS from baseline Visit 2 (Week 0) to Visit 5 (Week 12), Visit 7 (Week 24), and Visit 10 (Week 52)
- Tanner pubertal stage at baseline Visit 2 (Week 0), Visit 5 (Week 12), Visit 7 (Week 24), Visit 9 (Week 40), and Visit 10 (Week 52)

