2 STUDY OBJECTIVES

2.1 Primary objectives

The primary objectives of the study are:

- To assess the effect on glycemic control, as measured by HbA1c, of EQW following 24 weeks of treatment compared to placebo in children and adolescents with type 2 diabetes mellitus
- To evaluate the safety and tolerability of EQW compared to placebo following 24 weeks of treatment in children and adolescents with type 2 diabetes mellitus

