- Following the controlled assessment period, all patients enter a 28-week extension period. Group A patients will continue to receive EQW for an additional 28 weeks up to Visit 10 (Week 52). Group B patients will initiate treatment with EQW for 28 weeks up to Visit 10 (Week 52). During the 28-week extension period, patients will be required to return to the clinical study site at 6-, 10-, and 12-week intervals at Visit 8 (Week 28), Visit 9 (Week 40), and Visit 10 (Week 52) for efficacy, safety, PD, and PK assessments.
- At Week 26 of the controlled assessment period, patients will be contacted by phone by qualified study-site personnel to discuss study compliance, address any questions related to study medication, and review AEs
- Patients who withdraw from the investigational product after Visit 2 (Week 0) and prior to Visit 10 (Week 52) will be invited to return to the study site for an Early Termination visit for HbA1c, fasting plasma glucose, body weight, and clinical safety laboratory measures.
- All visits scheduled during the 24-week controlled assessment and 28-week extension period should occur within ± 2 days of the scheduled date relative to Visit 2 (Week 0).
- All patients will return to the site on Visit 11 (Week 62/Study Termination).

A detailed schedule of study procedures by visit is presented in [Table 1](#) (Study Plan).

Table 1
Study Plan

Evaluation	Visit 1 Screening	Controlled Assessment Period 24 weeks										Extension Period 28 Weeks			Visit 11 Week 62* (Study Termination)	Early Termination	
		Visit 2 Week 0	Week 2 Phone Call	Visit 3 Week 4	Visit 4 Week 8	Visit 5 Week 12	Visit 6 Week 16	Week 16 Phone Call	Visit 7 Week 18	Visit 7 Week 24	Week 26 Phone Call	Visit 8 Week 28	Visit 9 Week 40	Visit 10 Week 52 (End of Study Treatment)			
Fast (≥8 Hours Prior to Visit)	X	X	X	X	X	X	X	X	X	X	X	X	X	X	X	X	X
Informed Consent/Patient Assent/HIPAA	X																
Review of Inclusion and Exclusion Criteria	X	X															
Randomization		X															
Complete Medical History/Urine Drug and Alcohol Screen	X																
Adverse Event Assessment		X	X	X	X	X	X	X	X	X	X	X	X	X	X	X	X
Concomitant Medication Review	X	X	X	X	X	X	X	X	X	X	X	X	X	X	X	X	X
Physical Examination		X			X									X			X
ECG		X															
Body Weight, Height, and Vital Signs	X	X	X	X	X	X	X	X	X	X	X	X	X	X	X	X	X
Blood Sample for Serum βHCG Test (Females)	X															X	X

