6.2.3.7 Visit 7 (Week 24) – (Controlled assessment period)

Prior to Visit 7 (Week 24), patients will have fasted overnight (≥ 8 hours). If the study visit is scheduled on the same day as the patient's weekly administration of study medication, patients should delay administration of study medication on the morning of the study-site visit and bring the study medication to the site.

All patients will undergo the following procedures:

- Review of concomitant medication and AEs
- Body weight, height, and vital signs will be measured
- Urine will be collected for:
 - Pregnancy test (females only)
 - Urinalysis
 - N-telopeptide.
- Assessment of Tanner pubertal stage
- Injection site reaction assessment will be performed
- Blood samples will be collected for:
 - Chemistry and hematology
 - HbA1c
 - Fasting plasma glucose
 - Fasting insulin
 - Fasting lipids (TC, HDL-C, LDL-C, and TG)
 - TSH, FSH, LH, total testosterone, SHBG, estradiol, free T4, prolactin, cortisol, IGF-1, DHEAS, and bone specific alkaline phosphatase
 - Measurement of antibodies to exenatide
 - Measurement of plasma exenatide.
- Patients will receive diet and nutritional counseling
- Patients will have a study medication compliance review

- Study medication will be dispensed
- Patient and/or parent/caregiver will administer study drug at the study site (if applicable)
- Patients will be asked to return used/unused study medication.

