12.2.5 Exploratory safety endpoints

- Change in CEA from baseline Visit 2 (Week 0) to Visit 5 (Week 12) and Visit 10 (Week 52)
- Change in bone specific alkaline phosphatase and N-telopeptide from baseline Visit 2 (Week 0) to Visit 5 (Week 12), Visit 7 (Week 24) and Visit 10 (Week 52)
- Change in FSH, LH, FSH/LH, total testosterone*, SHBG*, and estradiol from baseline Visit 2 (Week 0) to Visit 5 (Week 12), Visit 7 (Week 24), and Visit 10 (Week 52)

*Change in total testosterone and SHBG also at Visit 9 (Week 40). Free testosterone will be calculated from total testosterone and SHBG values at Visit 5 (Week 12), Visit 7 (Week 24), Visit 9 (Week 40), and Visit 10 (Week 52).

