4.3.3 Visit assignment for safety variables

Below tables provide day windows for vital signs, safety lab parameters (clinical chemistry/hematology), and growth and development hormones.

Table 3.5 Visit Windows: Vital signs

Visit	Analysis Visit	Week	Period	Target Day	Day range
2	0	0	CAP	1	Baseline
3	1	4	CAP	29	2-42
4	2	8	CAP	57	43-70
5	3	12	CAP	85	71-105
6	4	18	CAP	127	106-147
7	5	24	CAP	minimum (last day of CAP or 169)	148 to last day of CAP
8	6	28	EP	maximum (last day of CAP+1 or 197)	last day of CAP +1 to 238
9	7	40	EP	281	239-322
10	8	52	EP	minimum (last day of EP or 365)	323 to last day of EP

CAP: Controlled assessment period. EP: Extension period.

Table 3.6 Visit Windows: Injection site reaction

Visit	Analysis Visit	Week	Period	Day range
3	1	4	CAP	1-42
4	2	8	CAP	43-70
5	3	12	CAP	71-105
6	4	18	CAP	106-147
7	5	24	CAP	Subjects not entering EP: 148 to last day of CAP
				Subjects entering EP: 148 to last day of CAP -1
8	6	28	EP	Subjects not entering EP: last day of CAP +1 to 238
				Subjects entering EP: last day of CAP to 238
9	7	40	EP	239-322
10	8	52	EP	323 to last day of EP

CAP: Controlled assessment period. EP: Extension period.

Table 3.7 Visit Windows: Total testosterone, SHBG, Tanner Pubertal Stage

Visit	Analysis Visit	Week	Period	Target Day	Day range
2	0	0	CAP	1	Baseline
5	3	12	CAP	85	2-126
7	5	24	CAP	minimum (last day of CAP or 169)	127 to last day of CAP
9	7	40	EP	maximum (last day of CAP+1 or 281)	last day of CAP +1 to 322
10	8	52	EP	minimum (last day of EP or 365)	323- last day of EP

CAP: Controlled assessment period. EP: Extension period.

Table 3.8 Visit Windows: Laboratory (hematology, clinical chemistry, urinalysis), Growth and development hormones such as TSH, FSH etc., Bone specific Alkaline phosphatase and N-telopeptide.

Visit	Analysis Visit	Week	Period	Target Day	Day range
2	0	0	CAP	1	Baseline
5	3	12	CAP	85	71-126
7	5	24	CAP	minimum (last day of CAP or 169)	127 to last day of CAP
10	8	52	EP	minimum (last day of EP or 365)	last day of CAP +1 to last day of EP

CAP: Controlled assessment period. EP: Extension period.

Table 3.9 Visit Windows: calcitonin, pancreatic amylase, lipase, CEA

Visit	Analysis Visit	Week	Period	Target Day	Day range
2	0	0	CAP	1	Baseline
5	3	12	CAP	minimum (last day of CAP or 85)	71 to last day of CAP
10	8	52	EP	minimum (last day of EP or 365)	last day of CAP +1 to last day of EP

CAP: Controlled assessment period. EP: Extension period.

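### Calcitonin, pancreatic amylase, lipase and CEA have one scheduled post-baseline sample against placebo, at Week 12, and none at the end of the 24-week controlled period

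*Protocol*

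**What the plan says.** Protocol 2.1 gives the second primary objective as "To evaluate the safety and tolerability of EQW compared to placebo following 24 weeks of treatment".

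Protocol 12.2.4 sets the thyroid and pancreatic marker endpoint as "Change in calcitonin, pancreatic amylase, and lipase from baseline Visit 2 (Week 0) to Visit 5 (Week 12) and Visit 10 (Week 52". Protocol 12.2.5 does the same for the exploratory marker: "Change in CEA from baseline Visit 2 (Week 0) to Visit 5 (Week 12) and Visit 10 (Week 52". SAP 3.4 and 3.5 repeat both. The hormone endpoint in Protocol 12.2.4 has three time points: "to Visit 5 (Week 12), Visit 7 (Week 24), and Visit 10 (Week 52".

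The visit lists agree with the endpoint lists. Protocol 6.2.3.7 has blood taken at Visit 7 (Week 24) for chemistry and hematology, fasting lipids, and "TSH, FSH, LH, total testosterone, SHBG, estradiol, free T4, prolactin, cortisol, IGF-1, DHEAS, and bone specific alkaline phosphatase". None of the four markers is on that list. SAP 4.3.3 also has no Week 24 row in "Table 3.9 Visit Windows: calcitonin, pancreatic amylase, lipase, CEA", whereas Table 3.8, for the other laboratory tests, has one.

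The control arm changes treatment at Week 24. Protocol 3.1 says: "Group B patients will initiate treatment with EQW for 28 weeks up to Visit 10 (Week 52".

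**The concern.** Protocol 1.3.1 itself discusses rat thyroid C-cell tumours and post-marketing pancreatitis. Calcitonin, amylase and lipase are the laboratory markers nearest to those risks, yet TSH, cortisol, IGF-1 and the bone markers are sampled at the end of the placebo-controlled period and these are not. A marker effect that appears only between Weeks 12 and 24 would have no scheduled placebo comparison. Placebo patients also have no scheduled value in the 12 weeks before their first EQW dose. Their change at Week 52 is taken from the Week 0 baseline, because SAP 3.6.1 does not re-derive baseline for the extension. It therefore combines 24 weeks of placebo with 28 of EQW.

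As context only, the change log in Appendix I shows that these markers used to be drawn at the visit that closed a 14-week controlled period. When that period became 24 weeks, the hormones gained Visit 7 and these markers stayed at Visit 5. No reason is given. This is consistent with an oversight but does not prove one.

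**Working it through.** The plan states no power or precision for these markers. Its only main-study power figure is for HbA1c (Protocol 12.7). An exact two-sample t calculation with 50 and 20 patients, difference 0.7, SD 1.0 and two-sided 0.05 gives 74.2%, matching the stated 74%. That check supplies the arm sizes used in step 5 and has no other bearing here.

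1. **Scheduled samples.** I used the visit lists in Protocol 6.2.3, because the columns of Table 1 cannot be read reliably in the text copy.
   - All four markers: Week 0, Week 12, Week 52, and Early Termination (which shares the Visit 10 list).
   - Calcitonin also at screening and Week 62.
   - Calcitonin and CEA also six-monthly in the off-drug Extended Safety Follow-up Period (Appendix E), for selected patients.
   - Scheduled, post-baseline, with the control arm on placebo: Week 12 only.

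2. **Share of the controlled period after the last such sample.** (24 − 12)/24 = 50%. As an illustration, Protocol 1.1 says concentrations build up over about 6 to 8 weeks. On that figure Week 12 falls 12 − 8 = 4 to 12 − 6 = 6 weeks after build-up, and Week 24 falls 24 − 8 = 16 to 24 − 6 = 18 weeks after. The figure is not specific to adolescents, and Protocol 3.3.2.1 reports faster exenatide elimination in them.

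3. **Early Termination samples.** Table 3.9 gives Week 12 a target of day 85 (or the last controlled day, if earlier) and a range from day 71 to the last day of the controlled period. SAP 4.3.4.1 selects the value closest to target. A patient who stops at, say, Week 20 normally keeps the Week 12 value. If that value is missing, the later sample is reported as Week 12. Neither case gives a Week 24 comparison.

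4. **Week 52.** Group A has had 52 weeks of EQW and Group B 52 − 24 = 28. No concurrent placebo group remains.

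5. **Precision of an added Week 24 sample.** With 50 and 20 patients, the 95% half-width is t(0.975; 68) × √(1/50 + 1/20) × SD = 1.996 × 0.2646 × SD = 0.53 SD. The difference detectable with 80% power is about 0.75 SD.

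**The case against.** The protocol and SAP agree with each other, so this is a design choice and not a contradiction. Several parts of the case against it stand.

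- A reader might infer that the primary safety objective cannot be met at 24 weeks. The documents do not support that. SAP 3.4 ties the objective to treatment-emergent adverse events, antibodies, examinations, general laboratory measurements and vital signs. The markers are separate bullets, and CEA is exploratory, with Protocol 6.4.5.5 calling its utility in adolescents unknown. Pancreatitis and thyroid cancer would be recorded as adverse events, which are compared with placebo over the whole controlled period.
- A reader might put a number on the dilution at Week 52, such as 24/52 = 46% of the effect recovered if it grows linearly with exposure, or 0% if it is a stable shift. Both effect shapes are assumptions found nowhere in the documents. A stable shift already present by Week 12 would be seen at Week 12.
- The planned marker summaries are descriptive (SAP 4.2.4, 4.2.4.4), and SAP 4.1.1 labels the second arm Placebo -> EQW. A careful reader is told that treatment has switched, although nothing says that the two Week 52 columns are not a placebo comparison.
- The SAP is dated 21 May 2020, and its Section 5 already cites the number of patients rescued at Week 24. Many Week 24 visits have probably passed, which limits who can gain from a new sample.

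None of this supplies a scheduled placebo-controlled value after Week 12.

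**Conclusion.** The point holds as a limited one. Three safety markers and one exploratory marker have no scheduled placebo-controlled measurement in the second half of the controlled period (12 of 24 weeks), although blood is already drawn at Visit 7. It would be wrong to say that the markers are measured only at Weeks 12 and 52, because other draws exist; those draws do not fill this gap. The Week 52 columns may understate an EQW effect, but by how much depends on how any effect develops with exposure, which the documents do not say.

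The 50% figure rests only on the visit schedule. The 0.53 SD figure assumes 50 and 20 patients with a Week 24 value and a common SD. It shows that an added sample would support description, not a firm conclusion. This is a cheap improvement, not a fault in the primary analysis.

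**What to change.** **Patients not yet at Week 24.** Add calcitonin, pancreatic amylase, lipase and CEA to the existing Visit 7 draw, before the first open-label dose. Add Visit 7 (Week 24) to Protocol 6.2.3.7, 12.2.4 and 12.2.5, to the Study Plan table, and to SAP 3.4 and 3.5. Split SAP Table 3.9 on the pattern of Table 3.8: Week 12 as days 71 to 126, and Week 24 as day 127 to the last day of the controlled period. The split is needed because, under the present table, a Week 24 sample would fall in the Week 12 window and normally lose to the sample nearer day 85. Present the Week 24 row only if scheduled Week 24 samples exist. A row filled only by Early Termination samples would describe a selected group.

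**Patients already past Week 24.** State in SAP 4.2.4.4 that the placebo comparison of these markers is at Week 12 only, and that the Week 52 EQW and Placebo -> EQW columns are not a randomized comparison of EQW with placebo.

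**Cost.** Four more analytes on an existing fasting draw, a few mL of blood per patient, a short amendment and one added table row. No new visit is needed. For patients past Week 24 the cost is two sentences in the SAP.
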